6.5.2. Prohibited Medicines

Medication listed in the exclusion criteria (see Section 5.2.2) will be prohibited up to Week 52.

To consider a subject who is currently taking any prohibited therapies for potential inclusion in this study, the Investigator must ensure that the subject has sufficient washout time prior to screening (see Section 5.2.2).

Strong CYP3A inhibitors or inducers are prohibited up to 4 weeks after end of treatment in view of the add-back treatment (APPENDIX H).

OATP1B1/1B3 inhibitors (e.g. clarithromycin, erythromycin, gemfibrozil, telithromycin) are prohibited during the treatment period only (APPENDIX I).

When a prohibited medication or treatment is necessary for the subject's well-being, the Sponsor must be notified and possible alternatives are to be discussed before administration of the prohibited medication or treatment whenever possible.

6.5.3. Non-Drug Therapies

Not applicable.

6.6. SUBJECT COMPLETION AND WITHDRAWAL

6.6.1. Subject Completion

For the first treatment period (primary endpoint), a subject will be considered as a "completer" when she has completed all study procedures at the Week 24 visit as described in the protocol.

For the second treatment period, a subject will be considered as a "completer" when she has completed all study procedures at the Week 52 visit as described in the protocol.

6.6.2. Subject Withdrawal from Study

Subjects will be informed that they have the right to withdraw from the study at any time, without prejudice to their medical care, and that they are not obliged to state the reason(s). Any withdrawal must be fully documented in the eCRF exit form and should be followed up by the Investigator.

The Investigator may withdraw a subject at any time if this is considered to be in the subject's best interest.

In addition, the Sponsor could make a decision to temporarily or permanently discontinue the study for safety, ethical, compliance or other reasons. In this case, the subject's participation may be ended prematurely without asking for her consent.

Subjects discontinuing participation in the study between Day 1 and Week 24 visits should undergo the procedures required at Week 24 visit, except the DXA in case of premature discontinuation occurring during the first four weeks of treatment. Subjects discontinuing participation in the study between Week 24 and Week 52 visits should undergo the procedures required at Week 52 visit, except the DXA in case of premature discontinuation occurring less than four weeks after Week 24. Subjects discontinuing participation in the study between Week 52 and Week 64 visits should undergo the procedures required at Week 64 and Week 76 visits if more than one month since the last BMD measurement.

Subjects who withdraw from the study before receiving the study drug will not require any further study procedures to be performed. The eCRF exit form should be completed.

6.6.2.1. Discontinuation criteria

During the course of the study, the subject may be discontinued for the following reasons to be reported in the eCRF Study Termination Form:

-	Lack of Efficacy:	Investigator's judgment only. If subject's opinion only, check subject's Request. Explain in the specify field.
-	Adverse Event:	Includes clinically significant new or worsening existing condition as judged by the Investigator. Document also in the AE form.
-	Subject's Request:	Consent withdrawal, subject moved, schedule conflicts, etc. Specify the reason in the comment section of the eCRF Exit Form.
-	Protocol Violation:	Major protocol violation which may affect the subject's safety. Specify the protocol violation in the comment section of the eCRF Exit Form.
-	Lost to Follow-up:	Document with two phone calls and a certified letter requesting return receipt without response. Document in the comment section of the eCRF Exit Form.
-	Pregnancy:	Subjects that have been exposed to study treatment and who become pregnant during the treatment period will be immediately withdrawn from treatment. Pregnancies that have been exposed to study treatment and/or started before the Week 64 visit or in case of early withdrawal up to 4 weeks after treatment discontinuation will be followed up for pregnancy and neonatal outcomes at birth. Any pregnancy must be reported with the Pregnancy Surveillance Form (see section 8.6).
-	Other:	Specify in the Comments section in the eCRF Exit Form. This reason should only be used if the reason for discontinuation is not better accounted for by another category.

Subjects presenting with alanine aminotransferase (ALT), aspartate aminotransferase (AST), gammaglutamyl transpeptidase (GGT) or total bilirubin ≥ 2 times the upper limit of normal at Day 1 will have to discontinue study treatment once these results are received by the study site. Subjects presenting with a Z-score \leq -2 assessed on the DXA at Day 1 will have to discontinue study treatment.

Subjects presenting with a clinically significant finding in the biopsy sample collected at screening and who have completed Day 1, will have to discontinue study treatment.

Subjects who have an elevation of hepatic enzymes suggesting drug induced liver toxicity according to the Food and Drug Administration (FDA) guidance on drug-induced liver injury, i.e. LFT increase $> 3 \times ULN$ associated with increased total bilirubin $> 2 \times ULN$ or INR >1.5, will be immediately withdrawn from treatment and followed up until return to normal of hepatic parameters.

At the central reading of the DXA scan at Week 24, if there is more than a 5% BMD loss on any one parameter a repeat DXA scan will be requested. If the repeat shows more than 8% loss at either femoral neck, hip or spine or a Z-score \leq -2.5, the subject will be required to stop treatment (see section 6.4.5).

All subjects withdrawn from treatment due to loss of BMD will have to complete the Week 76 assessments (urine pregnancy test, DXA scan and related AE follow-up) 6 months after treatment cessation.

6.6.2.2. Follow-up for discontinued subjects

For discontinued subjects, follow up data will be collected if the subject is willing to perform the follow up visits.

6.6.3. Subject Replacement

Discontinued subjects who received the study drug will not be replaced.

Discontinued subjects who did not receive the study drug may be replaced.

Discontinued subjects who had an exclusionary criterion, such as a Z-score ≤ 2 , or ALT, AST, GGT or total bilirubin ≥ 2 times the upper limit of normal, or a clinically significant biopsy finding, at Day 1 (treatment start) may be replaced.

7. INVESTIGATIONAL MEDICINAL PRODUCT

7.1. DESCRIPTION OF INVESTIGATIONAL MEDICINAL PRODUCTS

The term "Investigational Medicinal Product" (IMP) will refer to the ObsEva investigational drug OBE2109, the add-back (E2 1 mg/NETA 0.5 mg) or their matching placebo.

	Investigational Medicinal Product	Placebo	Add-back	Add-back Placebo
International nonproprietary name (INN)	NA	NA	Estradiol and Norethisterone Acetate	NA
Name of active ingredient	OBE2109	NA	E2 and NETA	NA
Form	Film-coated tablet	Film-coated tablet	Capsules	Capsules
Strength	100 mg	Placebo	1.0/0.5 mg	Placebo
Dose or concentration of active treatment	100 mg and 200 mg	0 mg	1.0/0.5 mg	0 mg
Route of administration	Oral			
Frequency of administration	Once daily for up to 52 weeks			
Manufacturer (Name and address)	Catalent Germany Schorndorf GmbH [name]		Sharp Clinical Services Inc. [name]	
Packaging (primary and secondary)	PVC/Al blister with 7 tablets per blister		PVC/Al blister with 7 capsules per blister	
secondary)	Aluminum pouch		Carton box	
Storage Requirements	ge As indicated on the study drug kit label			

7.2. DOSAGE AND ADMINISTRATION

Investigational Medicinal Products (IMPs)

OBE2109 and placebo treatments will be supplied as film-coated tablets for oral administration.

Add-back and placebo add-back will be supplied as capsules.

On Day 1, Week 12, Week 24 and Week 36, the subject will be given sufficient kits for 14 weeks (i.e. including two extra weeks).

At the Week 12, 24 and 52 visits, unused medication will be returned to the site. At Week 36, the subject will keep the kits that were provided at Week 24 as they will be needed to complete the treatment.

IMP treatment will start on Day 1 between the first and the seventh day of menstruation and will be administered once daily, up to about 52 weeks. The subjects will take 2 tablets(OBE2109/placebo), one from each blister, and 1 capsule (Add-back/placebo) ideally in the morning of each day as follows:

Treatment group	Daily dose Day 1 to Week 24		Daily dose Week 24 to Week 52	
Placebo OBE2100 Uplacebo add back	OBE2109 OBE2109 Add-back	Placebo Placebo Placebo	OBE2109 OBE2109 Add-back	Placebo Placebo Placebo
Placebo OBE2109 +placebo aud-back			OBE2109 OBE2109 Add-back	100 mg 100 mg E2/NETA
100 mg + placebo add-back	OBE2109	100 mg	OBE2109	100 mg
	OBE2109	Placebo	OBE2109	Placebo
	Add-back	Placebo	Add-back	Placebo
100 mg + add-back	OBE2109	100 mg	OBE2109	100 mg
	OBE2109	Placebo	OBE2109	Placebo
	Add-back	E2/NETA	Add-back	E2/NETA
200 mg + placebo add-back	OBE2109	100 mg	OBE2109	100 mg
	OBE2109	100 mg	OBE2109	100 mg
	Add-back	Placebo	Add-back	E2/NETA
200 mg + add-back	OBE2109	100 mg	OBE2109	100 mg
	OBE2109	100 mg	OBE2109	100 mg
	Add-back	E2/NETA	Add-back	E2/NETA

Add-back: E2 1 mg / NETA 0.5 mg

7.3. PACKAGING AND LABELLING

The study drug will be provided by the Sponsor (or delegate) as two separate 14-week kits to be dispensed at each time point: 1x OBE2109 or placebo kit and 1x add-back/placebo kit.

Each OBE2109 kit will contain 14 Aluminum (Al) pouches, each containing two PVC/Al blisters, i.e. sufficient to cover treatment for 14 weeks for each subject. All the 14 pouches and their corresponding blisters will be labeled with the same kit number, to be provided to a given subject. OBE2109 kit numbers will start with the letter B followed by 4 digits (B0001, B0002, etc).

The add-back kit will contain 14 blisters, i.e. sufficient to cover treatment for 14 weeks for each subject. All the 14 blisters will be labeled with the same kit number (different from the OBE2109 kit number), to be provided to a given subject. All add-back kits will begin with the letter N followed by 4 digits (N0001, N0002, etc)

Labels will be printed in the local language of the countries where the study will take place in accordance with applicable local regulations, the recommendations of GMP guideline (Annex 13) and FDA 21 CFR 312.6 part.

The label on the secondary packaging will indicate at least the following items:

- Protocol number
- Kit number
- Batch number
- Storage conditions
- Sponsor name and address

Label examples are filed in the study file at the Investigator's site and in the trial master file.

7.4. PREPARATION, HANDLING AND STORAGE

The investigational site will store the IMP according to the specifications of the sponsor. The IMP storage conditions will be indicated on each pouch and carton box.

The storage facility at site should be locked and temperature-controlled.

OBE2109 and add-back must be stored at 20°C to 25°C (68°F to 77°F), excursions permitted between 15°C and 30°C (between 59 °F and 86°F). The storage temperature at the clinical site must be recorded by using a minimum/maximum thermometer or electronically 24 hours a day with printouts available on request.

The IMP may be dispensed only by the pharmacist or by a member of staff specifically authorized by the Investigator.

Any deviations from the recommended storage conditions at the site should be immediately reported to the sponsor (or delegate), and the IMP should not be used until authorization has been given by the sponsor (or delegate).

7.5. IMP ACCOUNTABILITY

The Investigator is responsible for ensuring IMP accountability, including reconciliation and maintenance of drug records.

- 1. Upon receipt of the IMP, the Investigator (or pharmacist) will check for accurate delivery and acknowledge receipt. A copy of acknowledgement of receipt will be retained in the investigator file.
- 2. The dispensing of the IMP will be carefully recorded on the appropriate drug accountability booklet provided by the Sponsor (or delegate) and an accurate accounting will be available for verification by the study monitor at each monitoring visit.
- 3. IMP accountability records will include:
 - a. Confirmation of IMP delivery to the trial site
 - b. The inventory at the site of IMP delivered
 - c. The use of each dose by each subject
 - d. The return to the Sponsor (or delegate) or alternative disposition of unused IMP
 - e. Dates, quantities, batch numbers and kit numbers assigned to the subject
- 4. The Investigator should maintain records that adequately document:
 - a. The subjects were provided with the doses specified by the protocol/amendment(s)
 - b. All IMP provided were fully reconciled

Unused IMP must not be discarded or used for any purpose other than the present study. IMP that has been partially dispensed to a subject must not be re-dispensed to a different subject.

The Study monitor will periodically check the IMP accountability booklet and check all IMP dispensations and returns (both unused and used treatments) during the entire study period and prior to making arrangements for their return to the Sponsor (or delegate) or authorizing their destruction by the study site in agreement with the Sponsor.

7.6. ASSIGNMENT TO TREATMENT GROUPS

Subjects will be randomized to one of five treatment groups in a 1:1:1:1:1 ratio, using a permuted block randomization stratified by race to ensure that black subjects are evenly represented in all treatment arms. The randomization will determine which subjects from the placebo arm will be switched at Week 24 to the OBE2109 200 mg + add-back and which will remain in the placebo arm.

Prior to the start of the study, a randomization list and a treatment kit list will be generated by a designated statistician from the Sponsor or delegate to be transmitted to the assigned clinical packaging organization for labeling and for the set up of the IWRS.

Upon randomization in the IWRS, the site will be provided with the appropriate kits in time for the Day 1 visit which should take place at the earliest 7 days after randomization. The IWRS will provide the kit numbers, which will correspond to the OBE2109/placebo and add-back therapy/placebo kit

numbers. OBE2109 kit numbers will start from B0001, B0002, B0003 etc. (5-characters), while the add-back kit numbers will start with N0001, N0002, etc.

7.7. ASSESSMENT OF INVESTIGATIONAL MEDICINAL PRODUCT COMPLIANCE

Each subject must be instructed to take one tablet from each blister and one capsule daily. In addition, she must bring with her to each visit both opened and unopened IMP packages, in order to allow the assessment of compliance with study treatment.

The decision to withdraw a non-compliant subject from the study will be discussed between the Investigator and the Sponsor. A blind review meeting will take place prior to unblinding. Subjects with poor compliance and other significant protocol violations may be excluded from the Per Protocol Analysis Set.

During the entire study period, the study monitor will perform drug accountability and the assessment of compliance with study treatment by checking both opened and unopened IMP packages, as well as empty blisters.

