3. ENDPOINTS

3.1. EFFICACY ENDPOINTS

3.1.1. Primary

Reduced menstrual blood loss at 24 weeks of treatment (last 28 days prior to Week 24 visit) defined as menstrual blood loss \leq 80 mL and \geq 50% reduction from baseline.

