9.4. ANALYSIS SETS

The following data sets will be used for the statistical analysis:

- 1. **Safety Set:** All randomized subjects who received at least one dose of double-blind study drug irrespective of the treatment received. Subjects will be analyzed according to treatment received.
- 2. **Full Analysis Set (FAS):** All randomized subjects who received at least one dose of doubleblind study drug irrespective of the treatment received. Subjects will be analyzed according to randomized treatment.
- 3. Week 24 Per Protocol (PP) set: All subjects in the FAS excluding those identified as major protocol violators up to Week 24.
- 4. Week 52 Per Protocol (PP) set: All subjects in the FAS excluding those identified as major protocol violators up to Week 52.

As per the analysis set defined above, randomized subjects who withdraw from the study prior to treatment will not be included for the statistical analyses. As this is a double-blind study with a single centralized randomization list (stratified only by race) the decision of whether or not to begin treatment could not be influenced by knowledge of the assigned treatment.

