9.5.2. Primary Efficacy Analysis

The primary analysis set for the efficacy analyses will be the Full Analysis Set.

The primary analyses of reduced menstrual blood loss at 24 weeks of treatment (last 28 days prior to week 24 visit) will be analysed as a categorical variable (yes / no response) and will be conducted as follows:

Cochran-Mantel-Haenszel (CMH) tests with adjustment for the stratification factor race will be used to test the null hypothesis of no treatment effect for each OBE2109 group vs. placebo with regards to the

proportion of subjects with a reduced menstrual blood loss at 24 weeks. The odds ratios will be estimated from the CMH test together with the associated 95% CI and corresponding p-values. The proportion per treatment arm will be displayed together with exact Clopper-Pearson 95% CIs. The differences in percentages with corresponding 95% Newcombe-Wilson confidence intervals will also be presented. The homogeneity of the odds ratios will be explored using the Breslow-Day test.

In addition to the CMH tests and to further explore a possible interaction between race and treatment, a logistic regression model with terms for treatment, stratification factor race and the interaction between treatment and race will be fitted to the binary response data. Contrast and estimate statements will provide separated tests for each OBE2109 group vs. placebo for each strata. In case of too many empty cells or non-convergence of the model, separated Fisher's exact tests will be used for each comparison versus placebo, within strata. Subjects who discontinue prematurely due to lack of efficacy or adverse events, or who undergo operative or radiological interventions for uterine fibroids, will be considered as non-responders.

In order to account for multiplicity given four different OBE2109 treatment groups, each primary endpoint comparison versus placebo will be conducted at the 0.0125 level of significance, i.e. 0.05 divided by 4.

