9.5.5. Missing Data

In order to take into account all randomized subjects in the analysis, the assessment of the primary endpoint for subjects who do not have menstrual bleeding data up to Week 24 (and who did not discontinue prematurely due to lack of efficacy or adverse events, or undergo operative or radiological interventions for uterine fibroids) will be based on the results from the last 28 days prior to the last diary completion. Subjects who have less than 28 days of data will be treated as non-responders. The secondary endpoint of amenorrhea will be assessed in a similar way.

Missing values for continuous efficacy endpoints analyzed via likelihood methods (e.g. repeated measures mixed models) will not be directly imputed as they are handled within the analysis itself, under the assumption that the model specification is correct and that the data is missing at random.

Sensitivity analyses will be conducted to check the robustness of the analysis results under alternative assumptions with regards to missing data. Further details on the handling of missing values and planned sensitivity analyses will be defined in the SAP.

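### Section 7.7 lets poor compliance end study participation before Week 24, so an obtainable Week 24 outcome in the Full Analysis Set is replaced by a rule

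*Protocol*

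**What the plan says.** Section 7.7 provides for removal from the study, not only from treatment: "The decision to withdraw a non-compliant subject from the study will be discussed between the Investigator and the Sponsor". It gives no compliance threshold. The paragraph then adds that "Subjects with poor compliance and other significant protocol violations may be excluded from the Per Protocol Analysis Set".

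Section 9.5.2 states that "The primary analysis set for the efficacy analyses will be the Full Analysis Set". Section 9.4 puts every randomised and dosed woman in that set, whatever she actually took, and adds that "Subjects will be analyzed according to randomized treatment".

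The primary endpoint (Section 3.1.1) is read from the 28 days before the Week 24 visit. Section 6.3 bases all bleeding endpoints on alkaline hematin data.

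Without Week 24 data, two rules apply:

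- Section 9.5.2 makes non-responders of "Subjects who discontinue prematurely due to lack of efficacy or adverse events", and of women who have a procedure for fibroids. Non-compliance is not named.
- Section 9.5.5 says that the assessment of the others "will be based on the results from the last 28 days prior to the last diary completion". Those with fewer than 28 days of data are non-responders. Amenorrhea is assessed in a similar way.

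Section 6.6.2 has a woman who leaves before Week 24 undergo the Week 24 procedures at departure. Section 6.6.2.2 collects later data only if she is willing, and no section says that such data enter the primary endpoint.

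**The concern.** An as-randomised analysis needs the Week 24 outcome of poor compliers as much as anyone's. Section 7.7 lets the investigator and the sponsor end participation for a reason that does not prevent that outcome from being measured. A result that could have been observed is then replaced by an earlier window.

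Compliance arises after randomisation and may depend on the arm. Section 1.6 expects hypoestrogenic effects such as hot flushes at these doses, and links add-back to better adherence under GnRH agonists. A difference between arms with and without add-back is therefore plausible, though the protocol reports none.

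The primary endpoint is not the only one touched. Amenorrhea, time to amenorrhea and time to reduced blood loss, all to Week 24, are in the confirmatory sequence of Section 9.5. Under Section 9.5.3 a woman without amenorrhea by Week 24 is censored at her last hematin assessment, and time to reduced blood loss is analysed in the same way. Censoring brought about by poor compliance may be informative.

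**Working it through.** **1. The plan's own figure.** Section 9.2 gives 64 per arm for at least 90% power to reject all four comparisons, with 30% against 70% response and two-sided alpha 0.05/4 = 0.0125. Rejecting all four with 90% power needs at most 0.10/4 = 0.025 type II error per test, so 97.5% power each.

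- n = [z(0.99375)·√(2·0.5·0.5) + z(0.975)·√(0.3·0.7 + 0.7·0.3)]² / 0.4² = [2.498·0.7071 + 1.960·0.6481]² / 0.16 = 57.6, so 58.
- With continuity correction: (57.6/4)·[1 + √(1 + 4/(57.6·0.4))]² = 62.5, so 63.
- Exact joint power at 64 per arm with a shared placebo group: 0.945 (chi-square) or 0.922 (Fisher).

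The stated 64 is sound. The point concerns outcome handling, not sample size.

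**2. The route through the text** for a woman withdrawn for non-compliance before Week 24:

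| Step | Section | Result |
|---|---|---|
| Withdrawn from the study | 7.7 | Collection ends, apart from departure procedures and optional follow-up |
| Still in the primary set? | 9.4 | Yes, as randomised |
| Non-responder by reason? | 9.5.2 | No; non-compliance is not listed |
| 28 days of data or more | 9.5.5 | Scored on hematin data for the 28 days before the last diary completion |
| Fewer than 28 days | 9.5.5 | Non-responder |

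Withdrawal after Week 24 leaves the primary endpoint untouched.

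**3. Size, by assumption.** The protocol gives neither a non-compliance rate nor a withdrawal rate. Let w be the share of an active arm withdrawn for this reason, c the response rate under the carried window, and q the rate that Week 24 measurement would have shown.

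Overstatement of the arm's rate = w × (c − q)

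Take c = 70% (the planned active rate), and q = 30% (the planned placebo rate), 50% or 70%:

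| w | q = 30% | q = 50% | q = 70% |
|---|---|---|---|
| 2% | 0.8 points | 0.4 | 0 |
| 5% | 2.0 | 1.0 | 0 |
| 10% | 4.0 | 2.0 | 0 |
| 15% | 6.0 | 3.0 | 0 |

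The sign can also reverse. If the withdrawn women all had fewer than 28 days of data, then c = 0. With w = 5% and q = 30%, the arm is understated by 0.05 × 30 = 1.5 points.

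**4. Effect on the test.** At 100 per arm and alpha 0.0125, the power of one comparison is 0.9997 at 70% against 30%. With w = 15% and q = 30%, the measured rate is 0.85 × 70 + 0.15 × 30 = 64%, and power is 0.993. If the same 15% all counted as failures, the rate is 0.85 × 70 = 59.5%, and power is 0.962. For all four comparisons, with every active arm so affected, the lower bound 1 − 4 × (1 − power) is 0.973 and 0.849. The last figure is an outer limit, since neither the plan nor the proposal scores all these women as failures.

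**The case against.** The strongest reply is that the route is narrow and its effect unproven. Section 7.7 calls for a discussion and mandates nothing. Under Section 7.8 investigators know neither the allocation nor the on-treatment hematin results. Women who stop for adverse events or lack of efficacy are already non-responders, so the main tolerability and efficacy routes are penalised. Section 9.5.5 promises sensitivity analyses. The carry-forward rule also covers subject request and loss to follow-up, which a change to Section 7.7 leaves as they are. All this stands and limits the weight of the point. It does not remove it: blinding does not prevent bias from compliance that itself depends on the arm, and no sensitivity analysis recovers outcomes that were not collected.

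Three stronger readings are tempting, and the documents do not support them:

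- A reader might infer that she drops out of the FAS. Section 9.4 keeps her in it; only her Week 24 result is replaced.
- A reader might infer that Section 7.7 goes beyond the discontinuation list, because the protocol-violation reason in Section 6.6.2.1 is limited to a "Major protocol violation which may affect the" subject's safety. The same list has an Other category that can hold such a withdrawal.
- A reader might infer that the rule must favour poorly tolerated arms. Her last 28 days may already include the poor intake and, with a half-life of about 15 to 20 hours (Section 1.5.1), may already show weaker bleeding control. The gap could be zero, and the rule for fewer than 28 days works the other way.

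**Conclusion.** The point holds in a limited form. Withdrawal for non-compliance before Week 24 creates avoidable, possibly informative missing data in the as-randomised analysis of the primary endpoint, and affects amenorrhea and the time-to-event endpoints similarly. The direction is not certain. The 0 to 6 points for an active arm rest entirely on assumed withdrawal of 2% to 15%, a carried response of 70% and a Week 24 response of 30% to 70%; with at most 10% withdrawn the ceiling is 4 points. The estimate and its as-randomised meaning are at risk far more than the significance test. This is a cheap improvement worth making, not an error that undermines the trial.

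**What to change.** Replace the withdrawal sentence in Section 7.7 with wording such as: *Non-compliance alone does not end study participation or data collection. Non-compliant subjects are asked to continue visits, eDiary entries and alkaline hematin collection to Week 24 and Week 52. Compliance is addressed through the Per Protocol sets.*

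Add to Section 9.5.2 or 9.5.5 that hematin data collected in this way are used for the FAS endpoint, so that the 28-day rule applies only where they are truly missing.

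Safety decisions, any decision on study treatment under Section 6.6.2, and a woman's right to withdraw are unchanged.

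The cost is these sentences, a site instruction, and a few poorly compliant women remaining on the visit schedule. The change belongs in the protocol, because no later analysis plan can restore outcomes that sites were allowed to stop collecting.
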